12.2 Informed consent, where subject is unable to give informed consent (incapacity/emergency)

This study will not include such subjects.

13 ADVERSE EVENTS

13.1 Definition of adverse event (AE)

An adverse event (AE) is defined as any untoward medical occurrence, unintended disease or injury, or any untoward clinical signs in subjects, users or other persons, whether or not related to the study treatment.

This includes:

- Events related to the study treatment or the comparator
- Events related to procedures involved (any procedure in the research protocol)

13.2 Definition of serious adverse event (SAE)

Serious adverse event (SAE) is any event (whether or not associated with the study treatment) that:

- 1. Results in death
- 2. Lead to serious deterioration in the health of the subject that either resulted in
 - a) life threatening illness or injury, or
 - b) a permanent impairment of a body structure or a body function, or
 - c) in-patient or prolonged hospitalization, or
 - d) need of medical or surgical intervention to prevent life threatening illness or injury or permanent impairment to a body structure or body function.

NOTE: This includes events that might have led to a serious adverse event if

- a) suitable action had not been taken or,
- b) intervention had not been made or,
- c) the circumstances had been less fortunate.

	RESEARCH PROTOCOL
Version no 4.0	Clinical intervention study

These are handled under the SAE reporting system.

NOTE: Planned hospitalisation for a pre-existing condition, or a procedure required by the research protocol, without serious deterioration in health, is not considered a serious adverse event.

13.3 Reporting adverse events

Adverse events occurring during the study will be captured in the register and categorized according to the Clavien Dindo score. Patients will be followed according to the protocol, but with additional support as needed.

All adverse events shall be reported according to juridical guidelines for the actual hospital or nation.

13.4 List of foreseeable adverse events, anticipated adverse treatment/intervention effects.

Leaks, excess bleeding, and unintentional torsion of the gastric remnant could be potential adverse events. However, no increase in such events have been found in the very few studies published on this technique.

13.5 Emergency contact details for reporting SAEs

All adverse events will be entered into the register by the bariatric surgical team. In addition, unexpected serious adverse events shall be reported to the national coordinator by telephone at an early stage. The national coordinator will forward the report to the Principal Investigator (= the trial statistician, which is the statistician working in SOReg-N), and a decision will be made as to whether inform the DMC immediately or at the regular DMC-meeting that will occur every six months.

13.6 Data monitoring committee (DMC)

Members and terms of reference:

The DMC will have three members: Two experts (one surgeon and one medical gastroenterologist) with a special knowledge of LSG and reflux, and one statistician. The DMC shall:

- 1. Monitor the data from the trial and make recommendations to the TSC (following each DMC meeting) on whether there are any ethical or safety reasons why the trial should not continue.
- 2. Ensure that the safety, rights and well-being of the trial participants is given highest priority.
- 3. Determine if additional interim analysis of trial data should be undertaken.
- 4. Consider the data from interim analyses, unblinded if considered appropriate, plus any additional safety issues for the trial and relevant information from other sources.
- 5. Consider any requests for release of interim trial data and to recommend to the TSC on the advisability of this.
- 6. The DMC may be asked by the TSC to consider data emerging from other related studies.

	RESEARCH PROTOCOL
Version no 4.0	Clinical intervention study

DMC meetings:

The DMC shall meet every six months, or more often if deemed necessary. Meetings will be called for and organized by the Principal Investigator of the trial in association with the Chairperson of the DMC. Dates for DMC meetings should be agreed in advance, and only altered with agreement of all members. All significant communications between the Principal Investigator and the DMC shall be in writing, or if they have to be verbal, they should be backed up by written records.

The role of the DMC is to look at the (unblinded) data from an ethical standpoint, the safety rights and wellbeing of the participants being paramount. The DMC is the only body involved in the trial that has access to the unblinded comparative data.

DMC Processes

The Principal Investigator should prepare a comprehensive report for the DMC. This should be prepared and circulated well in advance of the meeting to allow DMC members time to study the data. The content of the report should be agreed in advance with the DMC Chairperson. The trial statistician may be invited by the Chairperson to attend part of the meeting to present the data; otherwise, no one involved with the trial or TSC should be present to see the unblinded data.

A full confidential report should be made in writing by the Chairperson of the DMC providing advice to the TSC on whether the trial should continue or not. It is the responsibility of the TSC to decide whether or not to act on the information received from the DMC.

Information provided by the DMC is likely to fall into the following categories:

- Information that might lead to the TSC stopping the trial prematurely in the event of a
 clear outcome if this is deemed to be appropriate in light of the accumulating data from
 the study or on the basis of information available from other sources.
- Information that might lead to the TSC modifying the design of the trial if this is deemed
 to be appropriate in the light of the accumulating data from the study or on the basis of
 information available from other sources.

	RESEARCH PROTOCOL
Version no 4.0	Clinical intervention study

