4 PROJECT METHODOLOGY

Hospitals performing more than 10 LSG annually will be invited to participate. A maximum of 200 patients will be accepted from any hospital. The start of the study is the date at which the first patient is operated. The inclusion of new patients will stop when 900 patients have been included (i.e. randomized), estimated to be reached after approximately two years. The number of included patients will be monitored continuously.

Evaluation of outcome will be based on data at two and five years postoperatively. Given an inclusion period of maximum two years, follow-up after two and five years, and another year for delayed follow-up and data processing, the project period will be for a maximum of eight years.

This study is an international, multicentre, randomized, triple-blind (blinded to patients, caregivers and researchers) prospective clinical intervention trial. For primary and secondary endpoints, analysis will be performed according to ITT. All patients will thus be analysed within the allocated group.

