5.1.5 Measures to minimise bias

The study is a multicentre study with participating hospitals from at least two countries (Norway and Sweden). Patients will be allocated by randomization, and patients, health care workers and investigators will be blinded. The surgeons operation note will state that "randomization was performed according to protocol" and will not contain information on whether gastropexy was performed or not. The study coordinator at each hospital will be responsible for keeping an updated list of patients participating in the study including who has received a pexy or not. This information must be stored at a safe place and in such a way that it can be made available for caregivers if deemed necessary. An updated list should be sent to SOReg-N on the first day of every month (see also 6.6.2).

All details regarding surgical technique except whether a pexy was performed or not must be registered in SOReg. To adjust for possible surgeon-related influence on outcome, a code number must be registered in SOReg for the individual main operating surgeon. A code number will be administered from SOReg-N to qualified surgeons whom will receive an envelope containing five numbers, and each participating surgeon within that hospital must draw one number after having been certified either by the study administrator or by a locally qualified surgeon. In Sweden the prefix for each number will be "S" and in Norway "N". The individual surgeon must use the same code number during the whole study period. Patients will be informed about the importance of follow-up both for clinical and investigational reasons. For PRO, one reminder will be send to non-responders.

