Each participating hospital will point out one person to coordinate the study within that hospital. This includes patient recruitment, obtaining written informed consent, local data management, correspondence with the national coordinator and with the Project Leader / institution responsible for this study. All included patients will be given a unique patient ID number. This number is the ID that is generated automatically by SOReg. All included patients in Sweden will thus have a six digits code number and all included patients in Norway will have a five digits code number. An updated list of included patients with overview of group allocation must be kept in a safe place within the hospital. A copy of this list containing the patient ID (no name or other identifiable data) shall be sent to SOReg-N on the first day of every month (see also 5.1.5 and 5.1.6 and appendix 17.6). Hospitals participating in the Bravo-arm of the study must balance the number of patients themselves so that an equal number of patients are allocated to the pexy and no-pexy group, respectively.

6.6.3 Factors that may compromise the outcome of the clinical study / interpretation of the results

This study is a randomized trial where the patients will be randomized into two groups. Potential differences between the groups like age, preoperative use of ARM and smoking will be accounted for by statistical methods.

Potential differences in performance between surgeons will be explored and adjusted for by statistical methods if found.

Missing values at two years will be accounted for by multiple imputation as necessary. Missing value at baseline will exclude the patient from the study.

Potential differences in culture and tradition between hospitals and countries for prescribing ARM, and similarly potential differences among patients demand for having ARM will be sought overcome by standardizing the information: ARM used in conjunction with the operation should be stopped at the latest by four weeks postoperatively. Patients using ARM after this period should actively be asked about this at the first follow-up (usually six weeks), and if no obvious reason exists it should be stopped. Similarly, if a patient is using ARM at the one-, two- or five year follow-up, the reason for this should be addressed.

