7 STATISTICAL CONSIDERATIONS

7.1 Statistical design

Patients will be allocated in a 1:1 fashion between LSG and LSGG. Participating hospitals will administer this by block randomization with 10 patients (i.e. 5 LSG, 5 LSGG) in each block. Group allocation will be determined by opening of sealed envelopes. The envelopes will be distributed to participating hospitals from SOReg-N.

All patients will be given a unique patient number, and SOReg-N will be informed regularly about group allocation.

Analysis for outcome will be performed according to ITT. All patients will thus be analysed within the allocated group. Missing data at two and five years will be handled by multiple imputation. The main analysis for outcome will be based on logistic mixed effect models with odds ratio between groups corrected for age, smoking and surgeon. A sensitivity analysis including hospitals will also be performed.

Information on group allocation will be blinded to patients and researchers.

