17.4 Bruk av syreblokkerande medisin

Retningslinjer for bruk av syreblokkerande medisin.

For pasientar som ikkje brukar syreblokkerande medisin før operasjon: Kan starte lågdose PPI (t.d. Somac 20 mgx1) like etter operasjon og bruke dette i inntil fire veker etter operasjon. Samstundes viktig å informere pasienten om at dersom problem med oppstøyt etter fire veker kan fastlege skrive ut ny resept.

For pasientar som brukar syreblokkerande medisin før operasjon: Kontinuer fram til operasjon. Start lågdose PPI etter operasjon og kontinuer i inntil fire veker. Samstundes viktig å informere pasienten om at dersom vedvarande problem med oppstøyt etter fire veker så kan fastlege skrive ut ny resept.

Alle tablettar (inkl PPI) som pasienten tek dei to første vekene etter operasjon må vere mindre enn ei ert for å unngå potensiell skade på stifterekka i magesekken. Tablettar som er større og som pasienten treng må delast eller knusast.

Ved kontrollar (6-vekers, eit år, to år, fem år): Dersom pasienten fortsatt brukar PPI eller anna syreblokkerande medisin, spør om dette. Vurder kvifor pasienten brukar PPI, om det er behov for å bruke PPI eller om pasienten kan trappe ned og slutte.

English text:

Guidelines for the use of acid-reducing medication (ARM):

For patients not using ARM before the operation: Patients may start a low dose PPI (like 20 mg pantoprazole once daily) just after the operation and use this for four weeks. The patient must be informed that if reflux symptoms persists after four weeks the doctor can write a new prescription.

For patients using ARM before the operation: Continue the use of ARM until the operation. After the operation the patient should use a low dose PPI for four weeks as above. The patient must be informed that if reflux symptoms persists after four weeks, the doctor can write a new prescription.

All tablets that a patient must use during the first two weeks after the operation (including PPI) must be smaller than a pea in order to avoid potential damage to the staple line. Tablets that are larger must be split into parts that are smaller than a pea.

	RESEARCH PROTOCOL
Version no 4.0	Clinical intervention study

At follow up (six weeks, one year, two years, five years): If the patient still uses PPI or other ARM, ask the patient about this. Evaluate why the patient is using ARM and whether this can be stopped.

17.5. Reoperasjon grunna refluks.

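### The protocol claims triple-blinding with only the DMC unblinded, but its own handling of the allocation list does not deliver this, so blinding of a judgement-dependent primary endpoint is only partly secured

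*Protocol*

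**What the plan says.** **The promise.** Section 4 describes the trial as "triple-blind (blinded to patients, caregivers and researchers) prospective clinical intervention trial". Section 5.1.5 says that "patients, health care workers and investigators will be blinded", and 7.1 says: "Information on group allocation will be blinded to patients and researchers". Section 13.6 adds: "The DMC is the only body involved in the trial that has access to the unblinded comparative data". Under 14.2, un-blinding the whole study needs the agreement of the TSC.

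**The procedures.**
- Sections 5.1.5 and 6.6.2: the study coordinator at each hospital keeps the list showing who did and did not receive a pexy. The same coordinator handles recruitment, consent and local data management.
- Section 6.6.2: hospitals in the Bravo subgroup must themselves make the two arms equal in number.
- Section 6.6.2 makes the transfer of the allocation list monthly: "A copy of this list containing the patient ID (no name or other identifiable data) shall be sent to SOReg-N on the first day of" each month. The form in 17.6 has separate lines for the SOReg IDs of pexy and no-pexy patients. Section 7.1 repeats that SOReg-N is kept informed of allocation.
- Section 13.5: unexpected serious adverse events are forwarded to the "Principal Investigator (= the trial statistician, which is the statistician working in SOReg-N"), after which it is decided when the DMC is told. Section 13.6 has the Principal Investigator prepare the DMC report and lets the trial statistician present the data.

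**The endpoint.** Under 5.1.2 a failure is daily ARM use due to dyspepsia in the last month, or reoperation due to GORD. At each follow-up visit, 17.4 instructs staff: "Evaluate why the patient is using ARM and whether this can be stopped". Sections 6.6.3 and 17.5 leave reoperation to clinical judgement within general guidance.

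**The concern.** Blinding matters here because the endpoint is not a purely mechanical record. Staff ask why a patient takes ARM, consider whether it can stop, and attribute the use to reflux or to something else. They also decide whether a reoperation is for GORD. Knowledge of the arm at any of these points could shift recorded failures in one direction and produce a difference that gastropexy did not cause.

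There are two separate routes. At the hospital, the person holding the list also manages the data, and the operating surgeon necessarily knows the arm. Centrally, the by-arm IDs arrive at the organisation where the Principal Investigator works. The first route bears on endpoint recording. The second bears on trial conduct, on SAE handling, and on whether a report could truthfully call the trial triple-blind with only the DMC unblinded.

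**Working it through.** **1. Promise against procedure**

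| Said to be blinded | What the procedures give |
|---|---|
| Health care workers and caregivers (4, 5.1.5) | The coordinator holds the by-arm list and does local data management (5.1.5, 6.6.2); the surgeon knows the arm |
| Investigators and researchers (4, 5.1.5, 7.1) | By-arm IDs go to SOReg-N monthly (6.6.2, 7.1, 17.6); the Principal Investigator works there (13.5) |
| Everyone except the DMC, for comparative data (13.6) | The Principal Investigator prepares the DMC report, and the trial statistician may present the data (13.6); 13.5 makes these the same person |

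Section 5.1.5 keeps pexy status out of SOReg. However, the monthly form uses the SOReg patient ID, which 6.6.2 makes the trial ID. Anyone with both the list and the register data for those IDs can form the comparison.

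No section bars a person who knows the arm from follow-up, from classifying the endpoint or from data entry.

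**2. The plan's own sample size**

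Inputs from 7.1 to 7.4: 14% v 7%, alpha 5% (taken as two-sided), power 85%, 1:1 allocation, 20% drop-out.

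n per arm = [1.960·√(2·0.105·0.895) + 1.036·√(0.14·0.86 + 0.07·0.93)]² / 0.07² = 342.8, rounded up to 343. The total is 686, and 686/0.8 = 857.5, rounded up to 858. Both stated figures reproduce, and nothing in this point changes them.

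**3. Sensitivity of the test to a false difference (illustration only)**

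Patients evaluable per arm: 900 × 0.8 / 2 = 360. Assume no true effect and a 14% failure rate in both arms. Suppose arm-aware handling removes 10% or 20% of recorded failures in the LSGG arm. These fractions are assumed; the protocol gives none.

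With d the false difference, SE0 the pooled and SE1 the unpooled standard error:

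P(reject) = Φ[(d − 1.96·SE0)/SE1] + Φ[(−d − 1.96·SE0)/SE1]

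- 14% v 12.6%: d = 0.014; SE0 = √(2·0.133·0.867/360) = 0.0253; d/SE0 = 0.55; P = 0.080 + 0.006 = 0.086.
- 14% v 11.2%: d = 0.028; SE0 = √(2·0.126·0.874/360) = 0.0247; d/SE0 = 1.13; P = 0.204 + 0.001 = 0.205.

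These false differences are 1.4/7 = 20% and 2.8/7 = 40% of the planned effect. Over a wider range, false differences of 1, 2, 3 and 4 points give rejection rates of about 7%, 13%, 23% and 38%.

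**The case against.** The case on the other side has real force.

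- **The recipient is not named.** The text sends the list to SOReg-N, not to the statistician by role. A reader might infer that the Principal Investigator receives it every month. Sections 13.5 and 13.6 make that likely, but no section states it.
- **A list of IDs is not comparative data.** Section 13.6 concerns outcomes by arm. The hospital list has a proper purpose, because caregivers may need it for subject-level un-blinding (5.1.5, 14.2). A statistician who prepares unblinded DMC reports is also normal practice. This stands. What remains is that 13.6 allows an exception to its own exclusivity sentence, and that 13.5 gives the same person the Principal Investigator title and a place in SAE handling while investigators are said to be blinded.
- **The central route does not reach ARM decisions.** No section gives the statistician patient contact or endpoint classification. This stands, so the two routes should not be merged into one claim of endpoint bias.
- **The coordinator is not said to classify the endpoint.** That is correct. A reader might also conclude that the endpoint is unprotected, but the documents do not support that. Patients are blinded, the operation note is silent on gastropexy, pexy is not entered in SOReg, and guidance on ARM and reoperation is common to all sites.
- **The bias figures are hypothetical.** They need a net shift in one direction across all hospitals. They show sensitivity, not expected bias.

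None of this reconciles the blinding statements with the procedures, or supplies the missing rule separating knowledge of the arm from endpoint recording.

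**Conclusion.** The concern holds in a limited form. The protocol's statements on who is blinded conflict with its own arrangements for the allocation list and the DMC report. This is a contradiction within the protocol, not detail that could be left to an SAP. Endpoint blinding is partly secured: there are genuine safeguards, but nothing keeps people who know the arm away from follow-up and recording.

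The contradiction rests on the text alone. The figures of about 9% and 20% rest on an assumed false difference of 1.4 or 2.8 points, no true effect, 14% in both arms and 360 evaluable per arm. They show that a distortion well below the planned 7 points would matter, not that one will occur. The point should be addressed, but the sample size and the endpoint definition can stay as they are.

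**What to change.** 1. In 5.1.5 and 6.6.2, give the by-arm list to an existing staff member with no follow-up, endpoint-recording or data-entry role. Keep the access that caregivers need for subject-level un-blinding (5.1.5, 14.2).
2. State that anyone who knows the arm, including the operating surgeon where possible, does not record ARM use, its reason or the reason for reoperation.
3. At SOReg-N, send by-arm IDs only to one designated unblinded person, separate from the Principal Investigator's SAE and trial-conduct roles.
4. Correct sections 4, 5.1.5, 7.1 and 13.6 so that they say who is unblinded and for what purpose.

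The cost is an amendment and a minor reassignment of tasks.

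Two further steps may suggest themselves and are not recommended. Taking two-year ARM status from the PRO questionnaire would change how the primary endpoint is ascertained and could add missing data, since 6.5.3 lets patients leave the PRO part alone and 5.1.5 provides one reminder. Requiring the DMC statistician to produce the by-arm tables would make a DMC member the author of what the DMC reviews.

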14 SUSPENSION OR PREMATURE TERMINATION OF THE CLINICAL STUDY

14.1 Criteria for suspension of the whole clinical study or in one or more sites

Potentially clinical relevant deviation in the number of serious events between the two groups (LSG – LSGG) will be discussed in the bi-annual meetings in the DMC. Similarly, interimanalysis will be performed on one-year follow-up data, and if differences in main outcome is found this will be addressed by the DMC. If the deviation is at one or a few sites only, these hospitals will be suspended until an explanation has been found. The steering committee will then decide whether or not to allow re-entry of this/these hospitals.

The study may be terminated by the representative for the research responsible institution or the investigator at any time. However, scheduled follow-up, as described in paragraph 6.6.4 and 6.6.5 should be continued for all subjects who were treated prior to termination of the study.

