5.1.4 Methodology

Data will be collected prior to the operation and at six weeks, one year, two years and five years after the operation. Clinical data, and answers to the PRO questionnaires will be collected and entered into the local register at these points except at six weeks where only data on complications will be entered. Data completeness at each time point will be assessed continuously at each hospital. Interim analysis will be performed every six month for 30 day complications, and every 12 months for primary endpoints.

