6.5.8 Time to select all subjects

The study will remain open for enrolment until the planned number of subjects is randomized (n=900), estimated to approximately two years.

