7.2 Sample size

LSGG are presently being performed in a small minority of hospitals in Norway, but the technique used differs between hospitals and surgeons making the results difficult to interpret. However, in order to avoid a potential influence from these hospitals on the power calculations, these hospitals have been excluded from this sample size evaluation.

The sample size calculation is based on stipulated changes in the use of ARM since we gather this as the most relevant known clinical variable reflecting patients symptoms.

According to recent, unpublished data from SOReg-S and SOReg-N, we find a three-fold increase in the use of ARM from preoperatively until two years after LSG for both countries. The prevalence of ARM-use before LSG however differs between the countries: In Norway, approximately 7% of the patients are using ARM on a daily basis while the corresponding figure in Sweden is approximately 5%.

In Norway, the use of ARM increase from 7 % to approximately 20 % as a mean observed at the two-year follow-up, while in Sweden the corresponding numbers are 5 % increasing to approximately 13%.

Since the population and number of hospitals performing bariatric surgery in Sweden is about twice that of Norway, we estimate a 2:1 composition of participants. Hence, the composite figures will be ≈ 6 % at baseline, increasing to ≈ 16 % at two years.

In order to account for a potential improvement in the LSG-group because of participation in a study (the Hawthorn-effect), the estimated rate for ARM-use in the LSG-group at two years will be set at 14 %.

	RESEARCH PROTOCOL
Version no 4.0	Clinical intervention study

According to the clinical experience encountered by [name] et al, adding gastropexy to the LSG reduced a rise in the use of PPI from preoperatively until two years. Stipulating a change from 6 to 14% in the LSG group, and from 6 to 7% in the LSGG-group, this will require a total of 686 patients using power 1 - beta = 85%.

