7.12 Min/max number of subjects per centre (multi-centre study)

The minimum number will be 10, and the maximum 200 subjects per center.

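### Section 14.1 makes suspension of a hospital mandatory on a local between-arm deviation with no threshold, reaches the main outcome as worded, and conflicts with DMC-only access to comparative data

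*Protocol*

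**What the plan says.** Section 14.1 names two things the DMC will consider. The first is safety: "Potentially clinical relevant deviation in the number of serious events between the two groups", taken up at the twice-yearly meetings. The second is joined to it by the word similarly and concerns an interim analysis of one-year data: "if differences in main outcome is found this will be addressed by the DMC". The next sentence is the rule at issue: "If the deviation is at one or a few sites only, these hospitals will be suspended until an explanation has been found". After that, "The steering committee will then decide whether or not to allow re-entry of this/these hospitals".

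The section states no size of difference, test, minimum number of patients or events, or direction.

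Other sections bear on the rule:

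- Section 5.1.4 sets the timing: "Interim analysis will be performed every six month for 30 day complications, and every 12 months for primary endpoints".
- Section 7.12 sets the site size: "The minimum number will be 10, and the maximum 200 subjects per center". No section gives the number of sites.
- Section 13.6 makes the DMC the sole body with unblinded comparative data, and leaves it to the TSC whether to act on DMC advice.
- Section 6.6.2 has each hospital keep a list of its patients with their allocation.
- Section 7.7 has group differences in complications discussed in the TSC.

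**The concern.** There are three difficulties.

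First, a difference between the arms in the main outcome is what the trial is designed to find. Seen at one hospital, it is the treatment effect plus sampling error. It does not point to a fault there, and a rule that waits for an explanation has no exit when the explanation is chance or the expected effect.

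Second, without a threshold, a hospital with a few dozen patients per arm can show a sizeable difference by chance.

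Third, suspending a hospital under this rule tells its staff, and the TSC that rules on re-entry, that its arms differ. The hospital also holds its own allocation list. The primary endpoint depends on decisions by patients and clinicians about acid-reducing medication, so knowledge of a local difference could influence it. The rule also prescribes an action that section 13.6 leaves to the TSC's discretion.

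**Working it through.** **The plan's own figure.** Section 7.2: "Stipulating a change from 6 to 14% in the LSG group, and from 6 to 7% in the LSGG-group"; section 7.3: alpha 5%, power 85%. Two-sided, pooled variance under the null, no continuity correction, mean rate (0.14 + 0.07)/2 = 0.105:

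n per arm = [1.960·√(2·0.105·0.895) + 1.036·√(0.14·0.86 + 0.07·0.93)]² / 0.07² = 342.8, so 343 per arm and 686 in total. Then 686/0.80 = 857.5, so 858. Both match sections 7.2 and 7.4, which confirms the rates used below.

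**Assumptions.** The number of sites is not given. The cap of 200 per centre implies at least 5 sites for 900 patients, and 5 to 30 are tried. Sites are of equal size and independent, with no dropout. The one-year rate is not given; 10.5% in both arms stands for no effect.

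**Chance of a large local gap, no true effect.** For each site, q is the exact binomial probability that the arms differ by 15 points or more. Over K sites the chance of at least one is 1 − (1 − q)^K. All patients are taken to have one-year data.

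| Sites × patients per arm | q | At least one site |
|---|---|---|
| 5 × 90 | 0.0011 | 0.5% |
| 10 × 45 | 0.0254 | 23% |
| 15 × 30 | 0.0569 | 58% |
| 20 × 22 | 0.0824 | 82% |

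The 15-point gap is an illustration, not a figure from the protocol. With 20 points, 15 × 30 gives q = 0.0207 and 27%.

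**A test per site.** If each site is tested at a true 5% level, 1 − 0.95^K gives 23%, 40%, 54%, 64% and 79% per look for 5, 10, 15, 20 and 30 sites. It passes 50% from 14 sites upward (1 − 0.95^13 = 49%; 1 − 0.95^14 = 51%). A Fisher test is conservative in small sites: with full data it flags at least one site in 15%, 19%, 14%, 27% and 17% of looks for the same site numbers.

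**If the planned effect is real.** At 14% v 7% with 45 per arm, a site reaches p<0.05 (z test) with probability 0.207. Over 10 sites that is 10 × 0.207 = 2.1 sites expected, and 1 − 0.793^10 = 90% for at least one. About two hospitals standing out while the others do not is the pattern the rule suspends, and here it comes from the treatment working as planned.

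**If an overall deviation must come first.** Suppose a pooled 5% test must be significant and some site must also show a 15-point gap. With no true effect, simulation of 100,000 trials gives about 4% (15 × 30), 5% (15 × 15) and 5% (20 × 22).

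**Serious events.** The protocol gives no rate; 2% to 4% is assumed, with 10 sites. At months 6, 12, 18 and 24 the chance that some site reaches z p<0.05 is 0/1/4/9% at a 2% rate and 0/7/19/31% at 4%. If a gap of two events counts as a deviation, it is 20/62/82/92% and 51/91/98/99%.

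**Timing.** Section 6.5.8: "planned number of subjects is randomized (n=900), estimated to approximately two years". One-year data begin to arrive at month 12. With annual main-outcome looks, the first informative one falls near month 24, when about half the patients have one-year data and enrolment is due to end. Data on all 900 arrive near month 36.

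**Passages side by side.** Section 13.6: comparative data stay with the DMC, and the TSC decides whether to act. Section 14.1: the hospital will be suspended because of a comparative result, and the TSC decides on re-entry. The TSC cannot judge whether a local difference has been explained without knowing that there is one.

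**The case against.** A reader might infer that chance alone will trigger suspensions at most interim looks. The protocol does not support that. Across plausible thresholds and site numbers the probability runs from about 1% (Fisher p<0.05, 30 sites, half the one-year data in) to near 100% (a 10-point gap, 15 or more sites). If many hospitals deviate at once, the condition of one or a few sites is no longer met.

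The rule may also be meant to apply only after an overall between-group deviation has been found and traced to particular hospitals. On that reading chance triggers are rare, as shown above. The text does not settle this.

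The word deviation is used in 14.1 for serious events, while the main-outcome sentence speaks of differences, so suspension could be read as a safety rule only. That is possible, but the main-outcome sentence is tied to the safety one and stands directly before the suspension sentence. The ordinary reading covers both.

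A reader might also infer that the rule would materially distort which hospitals recruit. For the main outcome the timing argues against this: informative looks come when enrolment is due to end. The serious-event trigger is the one active during recruitment, and its false-trigger rate depends on an event rate and a threshold that the protocol does not give.

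Finally, a DMC with a statistician exercises judgement, suspension is temporary and does not state the direction of the difference, and hospitals already hold their allocation lists. All of this is true and lessens the harm. None of it removes the mandatory wording or the conflict with 13.6.

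**Conclusion.** The point holds as a defect in a stated rule. Section 14.1 prescribes suspension with no threshold, as worded covers the effect under study, and cannot be carried out without disclosing a site-level comparative signal that section 13.6 confines to the DMC. It also mandates action that 13.6 leaves to the TSC.

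The false-trigger rate cannot be fixed. For a 15-point gap with no true effect it is 0.5% to 82% over the four layouts from 5 to 20 sites; for a nominal 5% test per site it is about 23% to 79% per look for 5 to 30 sites. These figures rest on equal independent sites, full one-year data for the gap figures, a one-year rate equal to the planning mean, and every site being examined without a prior overall signal. The blinding conflict depends on none of these assumptions and is the main reason to act. The effect on site mix through the main outcome is small unless recruitment overruns two years. An amendment is warranted.

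**What to change.** Amend section 14.1:

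1. Remove the main outcome as a ground for suspending a hospital. Examine site differences in it only at the final analysis, as treatment-by-site heterogeneity.
2. Replace automatic suspension with a DMC recommendation based on serious events or protocol conduct at the site, judged against the pooled rate and the variation expected by chance for a site of that size.
3. Reconcile 14.1 with 13.6, and with the TSC discussion of complications in 7.7, so that no site-level comparative result goes beyond the DMC and it is clear who decides on suspension and re-entry.

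The cost is protocol wording, with the TSC agreement and ethics approval that section 9 requires for any amendment. Sample size, data collection and the schedule of looks do not change, and the DMC keeps its power to act on a local safety problem.
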